6.2.6 Days in hospital and/or other health care unit

The length of a patient's hospital stay will be assessed by:

- the number of days the patient stayed in hospital at D30 and D90
- the number of days the patient stayed at another primary or rehabilitating health care unit after hospital discharge at D30 and D90.

6.2.7 *Days on haemodialysis*

The number of days on haemodialysis will be assessed at D30 and D90. Haemodialysis at D90 is considered permanent.

6.2.8 *Prevalence of compartment syndrome as measured by intra-abdominal pressure (IAP)*

Intra-abdominal pressure (IAP) is routinely measured during ICU stay via urine bladder catheter. IAP is recorded daily and a comparison of IAP between study groups is made.

6.3 **Safety Variables**

6.3.1 *Adverse Events*

6.3.1.1 *Collection of Adverse Events*

It is the responsibility of the Investigator to collect all AEs (both serious and non-serious) derived by observation, by spontaneous unsolicited reports of patients, and, where appropriate, by routine open questioning, e.g., “How have you felt since I last saw you?”

6.3.1.2 *Definitions*

Definitions of AEs and SAEs and their documentation and reporting within this study follow International Conference on Harmonisation (ICH) Good Clinical Practice, European Union, and national regulations and requirements (Clinical safety data management 1994).

An AE is defined as any untoward medical occurrence that occurs in a patient or clinical investigation subject administered a pharmaceutical product, and which does not necessarily have to have a causal relationship with this treatment. An AE can therefore be any unfavourable and unintended sign (including an abnormal laboratory finding), symptom or disease temporally associated with the use of an investigational product, whether or not it is considered related to the product.

All AEs up to D30 are collected. All AEs up to D30, which lead to death, are reported as SAEs. However, all deaths up to D90 will be reported as SAEs. Concomitant illnesses, which existed before entry into the study, will not be considered AEs unless there is any deterioration from baseline that is considered clinically relevant or significant during treatment or follow-up period until D30 or discharge from ICU. All AEs must be documented, regardless of the source of identification (e.g., physical examination, laboratory assessment, ECG, reported by patient).

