12.2 Secondary efficacy variables

The following secondary endpoints will be analysed:

- Time and reason/diagnosis of death up to D90 (3 months)
- Number of VFDs up to D30
- Number of days receiving hemodialysis at D30*
- Number of ICU free days up to D30*
- Organ failure free days up to D30
- Number of days in hospital up to D30 (length of stay in another health care facility)*
- Prevalence of abdominal compartment syndrome, i.e. intra-abdominal pressure (IAP) value differences between study groups
- Disability on D90 measured by modified ranking scale (mRS)
- Neutralizing (and anti-drug) antibodies IFN beta (ADAs and NAbs) in whole blood samples up to D30

*ICU free days and number of days in hospital, length of stay in another health care facility and number of days receiving hemodialysis at D90 summarized in pharmacoeconomic tables

All-cause mortality at D90 (3 months) will be compared using Cox regression model including stratification factors (if feasible). Estimated hazard ratios will be presented with associated 95% CIs and log-rank p-values for the FAS-E. Also, similar logistic regression as for the primary endpoint (D30 mortality) will be done.

For endpoints number of VFDs, number of ICU free days, organ failure-free days, number of days on hemodialysis, number of days in hospital, length of stay in another health care facility and IAP values, data will be summarised in terms of the mean, median, minimum and maximum, and the treatment groups will be compared using the Mann-Whitney U-test. Descriptive tables of IAP grade by timepoint will be presented using counts and percentages. Number of days on hemodialysis, number of days in hospital, length of stay in another health care facility and IAP value analyses will be performed for all patients and excluding deaths separately.

Complete data on organ failure free days may be unavailable due to SOFA scores not being assessed after ICU treatment. To account for this, the number of organ failure free days will be analysed by expressing these as a proportion of the days on which SOFA scores are available.

Disability measured with mRS will be summarized descriptively and the treatment groups will be compared using the Cochran-Mantel-Haenszel test for trend.

ADAs and NABs in whole blood samples up to D30 will be summarized using descriptive statistics.

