All secondary analyses are designed to be supportive of the analysis of the primary endpoint and there will be no adjustments for the multiplicity of endpoints so that each analysis will be undertaken at the two-sided 5% level of significance.

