19.3 Table and figure plan

Demographic Tables	
Table 14.1.1	Disposition of patients
Table 14.1.2.1	Demographics (categorical) (FAS-E)
Table 14.1.2.2	Demographics (categorical) (PPS)
Table 14.1.3.1	Demographics (continuous) (FAS-E)
Table 14.1.3.2	Demographics (continuous) (PPS)
Table 14.1.4.1	Major surgical outcomes affecting patient (FAS-E)
Table 14.1.4.2	Major surgical outcomes affecting patient (PPS)
Table 14.1.5.1	Surgical procedure and periprocedural information (FAS-E)
Table 14.1.5.2	Surgical procedure and periprocedural information (FAS-E)
Table 14.1.6.1	Medical history (FAS-E)
Table 14.1.6.2	Medical history (PPS)
Table 14.1.7.1	Concomitant medications/therapies (FAS-E)
Table 14.1.7.2	Concomitant medications/therapies (PPS)
Table 14.1.8	Pregnancy test (FAS-S)
Efficacy Tables	Efficacy
Table 14.2.1.1.1	All-cause mortality D30 (FAS-E)
Table 14.2.1.1.2	All-cause mortality D30 (PPS)
Table 14.2.1.2.1	Logistic regression of All-cause mortality D30 (FAS-E)
Table 14.2.1.2.2	Logistic regression of All-cause mortality D30 (PPS)
Table 14.2.1.3.1	All-cause mortality D90 (FAS-E)
Table 14.2.1.3.2	All-cause mortality D90 (PPS)
Table 14.2.1.4.1	Cox regression of All-cause mortality D90 (FAS-E)
Table 14.2.1.4.2	Cox regression of All-cause mortality D90 (PPS)
Table 14.2.1.5.1	Logistic regression of All-cause mortality D90 (FAS-E)
Table 14.2.1.5.2	Logistic regression of All-cause mortality D90 (PPS)
Table 14.2.1.6.1	Number of VFDs up to D30 (FAS-E)
Table 14.2.1.6.2	Number of VFDs up to D30 (PPS)
Table 14.2.1.7.1	Number of ICU free days up to D30 (FAS-E)
Table 14.2.1.7.2	Number of ICU free days up to D30 (PPS)
Table 14.2.1.8.1	Organ failure free days up to D30 (FAS-E)
Table 14.2.1.8.2	Organ failure free days up to D30 (PPS)
Table 14.2.1.9.1	Number of days on hemodialysis up to D30 (FAS-E)
Table 14.2.1.9.2	Number of days on hemodialysis up to D30 (PPS)
Table 14.2.1.9.3	Number of days on hemodialysis up to D30 excluding deaths (FAS-E)
Table 14.2.1.9.4	Number of days on hemodialysis up to D30 excluding deaths (PPS)
Table 14.2.1.10.1	Number of days in hospital up to D30 (FAS-E)
Table 14.2.1.10.2	Number of days in hospital up to D30 (PPS)
Table 14.2.1.10.3	Number of days in hospital up to D30 excluding deaths (FAS-E)
Table 14.2.1.10.4	Number of days in hospital up to D30 excluding deaths (PPS)
Table 14.2.1.11.1	Length of stay in another health care facility up to D30 (FAS-E)

Table 14.2.1.11.2	Length of stay in another health care facility up to D30 (PPS)

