Table 14.2.1.11.3	Length of stay in another health care facility up to D30 excluding deaths (FAS-E)
Table 14.2.1.11.4	Length of stay in another health care facility up to D30 excluding deaths (PPS)
Table 14.2.1.12.1	IAP values by timepoint (FAS-E)
Table 14.2.1.12.2	IAP values by timepoint (PPS)
Table 14.2.1.12.3	IAP values by timepoint excluding early deaths (FAS-E)
Table 14.2.1.12.4	IAP values by timepoint excluding early deaths (PPS)
Table 14.2.1.13.1	IAP grades by timepoint (FAS-E)
Table 14.2.1.13.2	IAP grades by timepoint (PPS)
Table 14.2.1.13.3	IAP grades by timepoint excluding early deaths (FAS-E)
Table 14.2.1.13.4	IAP grades by timepoint excluding early deaths (PPS)
Table 14.2.1.14.1	Disability on D90 measured with mRS (FAS-E)
Table 14.2.1.14.2	Disability on D90 measured with mRS (PPS)
Table 14.2.1.14.1	Neutralizing antibodies (FAS-E)
Table 14.2.1.14.2	Neutralizing antibodies (PPS)
	Pharmacodynamics
Table 14.2.2.1.1	MxA concentration (FAS-E)
Table 14.2.2.1.2	MxA concentration (PPS)
Table 14.2.2.2.1	MxA ANOVA (FAS-E)
Table 14.2.2.2.2	MxA ANOVA (PPS)
Table 14.2.2.3.1	CD73 concentration (FAS-E)
Table 14.2.2.3.2	CD73 concentration (PPS)
Table 14.2.2.4.1	CD73 ANOVA (FAS-E)
Table 14.2.2.4.2	CD73 ANOVA (PPS)
Table 14.2.2.5.1	Potential inflammatory markers (FAS-E)
Table 14.2.2.5.2	Potential inflammatory markers (PPS)
Table 14.2.2.6.1	PIM ANOVA (FAS-E)
Table 14.2.2.6.2	PIM ANOVA (PPS)
	Subgroup analyses
Table 14.2.1.1.1	All-cause mortality D30 by subgroups
Table 14.2.1.2.1	Logistic regression of All-cause mortality D30 by subgroups
	Safety Tables
Table 14.3.1	Extent of exposure and compliance (FAS-S)
Table 14.3.2	Summary of TEAEs (FAS-S)
Table 14.3.3.1	Treatment emergent adverse events (FAS-S)
Table 14.3.3.2	TEAEs by causality (FAS-S)
Table 14.3.3.3	TEAEs by severity (FAS-S)
Table 14.3.3.4	TEAEs by maximum severity (FAS-S)
Table 14.3.3.5	TEAEs by causality and severity (FAS-S)
Table 14.3.3.6	TEAEs by causality and maximum severity (FAS-S)
Table 14.3.4.1	TEAEs during treatment period (FAS-S)
Table 14.3.4.2	TEAEs during treatment period by causality (FAS-S)
Table 14.3.4.3	TEAEs during treatment period by severity (FAS-S)

Table 14.3.4.4	TEAEs during treatment period by maximum severity (FAS-S)
Table 14.3.4.5	TEAEs during treatment period by causality and severity (FAS-S)
Table 14.3.4.6	TEAEs during treatment period by causality and maximum severity (FAS-S)
Table 14.3.5.1	TEAEs during short-term follow-up period (FAS-S)

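### Hospital and other-facility days are tested as raw counts with no rule for death, so fewer days cannot be read as benefit if mortality differs between arms

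*SAP*

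**What the plan says.** SAP 12.2 lists hospital days, other-facility days and haemodialysis days among the secondary efficacy endpoints. For these, "the treatment groups will be compared using the Mann-Whitney U-test", and the analyses "will be performed for all patients and excluding deaths separately". There is no multiplicity adjustment, and "each analysis will be undertaken at the two-sided 5% level of significance". The table plan in SAP 19.3 carries both versions, for example Tables 14.2.1.10.1 and 14.2.1.10.3 for hospital days.

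The definitions are simple counts. Protocol 6.2.6 gives "the number of days the patient stayed in hospital at D30 and D90" and "the number of days the patient stayed at another primary or rehabilitating health care unit after hospital discharge". Protocol 6.2.7 says "The number of days on haemodialysis will be assessed at D30 and D90". None of the three has a rule for patients who die, and SAP 9.2 imputes nothing, so the count stops at death.

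Other endpoints do have such a rule. Under Protocol 6.2.3 to 6.2.5, a death before unassisted breathing gives zero ventilator free days, a death in the ICU gives zero ICU free days, and a death before reaching a SOFA score of zero gives zero organ failure free days. Hospital free days at D90 is named as a pharmacoeconomic endpoint, but it has no death rule and SAP 12.3.2 says it will not be analysed.

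**The concern.** A patient who dies in hospital on day 3 contributes about 3 hospital days and 0 other-facility days. In the all-patient ranking that looks like a better course than a survivor discharged on day 14. If the drug saves lives, the active arm keeps more patients who go on to use hospital days, and the test tends to point against it. If the drug raises mortality, the test tends to point in its favour.

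The version without deaths does not settle this. Death by D30 is the primary outcome and the thing the drug is meant to change, so removing deaths compares groups selected after randomisation. If the frailer patients both die more often and stay longer, the arm with fewer deaths retains more long stayers.

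Protocol 8.5.2 introduces the secondary endpoints as further confirmation of efficacy, and each version carries a p-value. A reader could easily take fewer days as a benefit.

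**Working it through.** **Inputs from the documents.** D30 mortality of 37% on placebo and 15% on active, and 86 active and 43 placebo evaluable patients (SAP 6). There were 35 evaluable patients at the interim after which the study stopped (SAP 2); the split 23:12 is assumed from the 2:1 ratio. Deaths within 36 hours are already outside FAS-E (SAP 8).

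**The plan's own figure.** A pooled two-proportion z-test at 37% vs 15%, 2:1, two-sided 0.05 and 80% power needs 44 + 88 = 132 patients; 43 + 86 gives 79.2% power. The stated 129 is reproduced closely, and the mortality rates can be used as they stand.

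**How many patients the exclusion removes.** Expected deaths are 43 × 0.37 = 15.9 on placebo and 86 × 0.15 = 12.9 on active. Excluding deaths drops 37% of one arm and 15% of the other.

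**Mean days, all patients.** Let survivors stay S days in both arms and deaths occur after D days in hospital. The arm mean is (1 − p)S + pD, and the difference, active minus placebo, is (0.37 − 0.15)(S − D) = 0.22(S − D).

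- S = 18, D = 6 (assumed): placebo 0.63 × 18 + 0.37 × 6 = 13.56; active 0.85 × 18 + 0.15 × 6 = 16.2; difference 2.64 days longer on active.
- S = 12, D = 12: difference 0.
- S = 24, D = 4: difference 4.4 days.

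The sign follows from deaths coming sooner than discharges; the size is a matter of assumption.

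**Mann-Whitney test, hospital days, simulated.** Survivor stays have the same distribution in both arms (lognormal, sigma 0.5, capped at 30), with an assumed median of 10 to 18 days and an assumed mean time to death of about 5 to 14 days. Nominal error is 2.5% per side.

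| Version | Link between death and stay | Against the drug, 86:43 | Against the drug, 23:12 |
|---|---|---|---|
| All patients | none | about 3–49% | about 2–16% |
| Excluding deaths | none | about 2% | about 2% |
| Excluding deaths | frailty, correlation 0.6, median stay 14 | about 15% | about 7% |

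The low end of the first row is the case of short stays and late deaths, where there is no distortion. A separate frailty run with an assumed median stay of 18 days gave 13% and 5.5% for the version without deaths.

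**Checks on direction.** With mortality reversed (86:43, median stay 14 days, deaths at about 9 days on average), the all-patient test shows significantly shorter stays on active in about 20% of trials. With equal mortality, both versions keep about 5% two-sided error.

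**Haemodialysis days.** Never-dialysed survivors score 0, so an early death without dialysis only ties with the best score, and dying patients may be dialysed more often. At 86:43, assuming 15% of survivors are dialysed:

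- 15% of deaths dialysed: no distortion (2.2% against the drug, 2.5% for it).
- 40% of deaths dialysed: 0.1% against, 10% for.
- 60% of deaths dialysed: 0.3% against, 21% for.

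The direction is not fixed.

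**The case against.** The strongest defence is that the all-patient test is a valid comparison of days used, which is a legitimate resource-use question, and that SAP 12.2 never says fewer days means benefit. That stands in part: with no mortality difference the test is sound, and what fails is the reading as efficacy. But the plan lists these endpoints under efficacy and gives no caution on reading them.

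It is also fair that both versions are shown beside D30 and D90 mortality, that SAP 12.2 calls the secondary analyses supportive, and that ventilator free and ICU free days already penalise many deaths. This lowers the severity. It does not make either day-count test answer the efficacy question when mortality differs.

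Three stronger readings are tempting, and the documents do not support them:

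- **That neither version can be unbiased.** Excluding deaths is unbiased when death is unrelated to stay. Its bias rests on a frailty link, which is plausible here but is an assumption.
- **That a life-saving drug would show more dialysis days.** The missing death rule is the same, but the direction is not established. Protocol 1.1 names acute renal failure among the causes of postoperative death, so the effect could run the other way.
- **That the intra-abdominal pressure tables share the fault.** Pressure is measured by timepoint; it is not a count that death cuts short.

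A death-penalised count also has a weakness: it partly re-tests mortality. For dialysis this is acute. With no dialysis effect at all, a test ranking deaths worst was significant for the drug in 69% of simulated trials at the planned mortality.

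**Conclusion.** The point holds for days in hospital and days in another health care facility, as a minor one. Both are tested at 5% on counts that stop at death, and neither planned version supports an efficacy reading if mortality differs, unless death and stay are unrelated, in which case the version without deaths is fair. For hospital days at the planned 37% vs 15%, the all-patient test is significant against a drug with no effect on survivors' stay in about 3 to 49% of trials at 86:43. At about the size reached when the study stopped (23:12), the figure is about 2 to 16%. These ranges rest on assumed stays and times to death, since the documents give none. Other-facility days were not simulated; there the concern is structural, because an in-hospital death scores 0. For haemodialysis days only the missing death rule is established.

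**What to change.** In SAP 12.2, make the tested comparison days alive and out of hospital (and out of other health care facilities) to D30, with patients who die by D30 scored zero or ranked worst. Label it a composite with mortality. This follows the logic of the ventilator free and ICU free day rules, though it is somewhat stricter: the ventilator rule credits days between weaning and a later death.

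Keep the raw all-patient and survivors-only tables for hospital, other-facility and haemodialysis days as descriptive summaries of resource use, without p-values. State whether the exclusion of deaths means deaths by D30 or by D90. Do not add a tested composite for haemodialysis.

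The cost is a few sentences in the SAP and one derived variable per tested endpoint. It uses data already planned for collection, and the SAP describes database lock as still to come. The downside is that the new result partly reflects mortality and must be read with the primary endpoint, not as separate evidence on length of stay.

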6.2 Methods and Timing for Assessing, Recording and Analysing Efficacy Parameters

6.2.1 *Mortality assessments*

The following mortality assessments are to be conducted:

- All-cause mortality at D30 and D90 (3 months)
- Kaplan-Meier survival curve to D90

Mortality is to be captured by assessing whether the patient is alive or dead and by recording the date of death and reason/diagnosis leading to death when available.

6.2.2 *Disability assessment*

Modified ranking scale (mRS) at D0 and D90 will be used to evaluate study subject disability. Single mRS value is applied for every patient based on patient or caregiver interview (Table 9). Pre-operation D0 mRS value is collected for reference (possible to collect also retrospectively by interview).

6.2.3 *Ventilator free days (VFDs)*

The number of VFDs at D30 will be assessed.

Definition of VFDs to D30:

VFDs to D30 is defined as the number of calendar days after initiating unassisted breathing (UAB) to D30 from first treatment, assuming a patient survives at least 48 consecutive hours after initiating UAB.

For example: If a patient initiates UAB on D16 and survives to D30, that patient would be assigned a VFD value of 14. If a patient initiates UAB on D16 but dies on D25 he/she would be assigned a VFD value of 9. If a patient survives for more than 48 hours after initiating UAB but then requires assisted breathing (for any reason) before D30 then the VFD value would be the total number of UAB days before D30 unless a period of assisted breathing was less than 24 hours and the purpose of

assisted breathing was a surgical procedure. Patients who die without initiating UAB will be assigned a VFD value of zero. All patients, whether still on or already off positive pressure ventilation, who are transferred to another hospital or healthcare facility prior to D30, will be followed up to assess the VFD outcome at D30.

Patients transferred to other health care facilities or to another hospital prior to D30 while still receiving assisted breathing/without assisted breathing will be followed until D30 to assess this efficacy measure. Unassisted breathing (UAB) is defined as any of the following:

- spontaneous breathing with face mask
- nasal prong oxygen or room air
- t-tube breathing
- tracheostomy mask breathing
- CPAP < 5 without pressure support (PS) or IMV assistance
- use of CPAP or BIPAP solely for sleep apnoea management

6.2.4 ***ICU free days***

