7.3 Sequential Organ Failure Assessment (SOFA)

SOFA scores are assessed daily from D0 post-dose to D30 whilst the patient is in the ICU and all daily elements of the SOFA score are available. **Note:** The worst daily value of each element should be used to calculate the overall SOFA score.

Table 8: Schedules for SOFAs

ASSESSMENTS	Baseline Period																							
	D0 pre-dose																							
SOFA																								

ASSESSMENTS	Treatment Period					
	D0 post dose	D1	D2	D3	D4	D5
SOFA	X	X	X	X	X	X

ASSESSMENTS	Short Term Follow-Up																								
	D6	D7	D8	D9	D10	D11	D12	D13	D14	D15	D16	D17	D18	D19	D20	D21	D22	D23	D24	D25	D26	D27	D28	D29	D30
SOFA	X	X	X	X	X	X	X	X	X	X	X	X	X	X	X	X	X	X	X	X	X	X	X	X	X

Table 9: Modified Ranking Scale (mRS)

The scale runs from 0-6, from perfect health without symptoms to death	
0	No symptoms
1	No significant disability. Able to carry out all usual activities, despite some symptoms
2	Slight disability. Able to look after own affairs without assistance, but unable to carry out all previous activities
3	Moderate disability. Requires some help, but able to walk unassisted
4	Moderately severe disability. Unable to attend to own bodily needs without assistance, and unable to walk unassisted
5	Severe disability. Requires constant nursing care and attention, bedridden, incontinent
6	Dead

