7.4.2 Screening Assessments and Pre-dose Procedures

7.4.2.1 **Screening assessments to be performed after diagnosis of RAAA prior to surgical treatment and the first dose of study medication**

Screening assessments will be carried out after informed consent is obtained and must be completed before the first dose of study medication is administered. **The first dose of the study medication is administered at arrival to the ICU (latest 4 hours after RAAA operation).**

The following parameters are reviewed and the data is recorded in the eCRF once the patient has been consented (refer to table 5 and the flow chart in figure 1):

- Date and time of informed consent
- Allocated patient screening number
- Medical history including:
 - chronic conditions
 - currently treated conditions
 - concomitant medications
- Review of the inclusion and exclusion criteria
- Demographic data including sex, age at entry and race
- Physical Examination of major body systems including predicted body weight (refer to Section 6.3.4 for the calculation formula) and height
- Recording of concomitant medications and therapies

The data must be collected during the screening assessment but can be entered in the eCRF after surgery.

7.4.2.2 Pre-dose procedures to be performed on D0 before the first dose of study medication is administered

On D0 all pre-dose procedures and assessments are to be performed **before the first dose of study medication**. **Note:** Where a patient's condition precludes an assessment taking place as scheduled, the assessment should be performed as soon as possible. If this is not possible, the assessment will not be performed and the reason for non-performance will be recorded. However, all D0 pre-dose assessments must be performed prior to the first dose of study medication being administered and every effort must be made to perform all assessments.

The following procedures and assessments are performed and the data is recorded in the eCRF (refer to the flow charts in Table 5):

- Review of the inclusion and exclusion criteria to ensure continued eligibility
- Randomisation: randomisation number and date and time of randomisation are recorded
- Hemodynamic collapse before cross clamping (yes/no)
- Vital signs (body temperature, blood pressure, pulse)
- Modified ranking scale (mRS) (evaluation of the value before surgery)
- Blood biochemistry (refer to Section 6.3.2 for specific biochemistry variables)

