9.1 Adjustment for covariates

The primary model will include the stratification factors (age group and gender) used in the randomisation as covariates.

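### The pre-operative mRS is collected but unused: a supportive baseline-adjusted D90 comparison would probably add precision, by an amount that depends on a correlation the documents do not give

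*SAP*

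**What the plan says.** Protocol 6.2.2 (Disability assessment) has the mRS scored at D0 and D90. Of the first it says "Pre-operation D0 mRS value is collected for reference", and it allows that value to be obtained later by interview. It adds that "Single mRS value is applied for every patient based on patient or caregiver interview". Protocol 7.4.2.2 lists the pre-surgery mRS among the D0 pre-dose procedures. The same section says that where an assessment cannot be done, "the assessment will not be performed and the reason for non-performance will be recorded". On scoring, Table 9 of the protocol states: "The scale runs from 0-6, from perfect health without symptoms to death". Death is therefore the worst category, 6.

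For the comparison, SAP 12.2 says "the treatment groups will be compared using the Cochran-Mantel-Haenszel test for trend". Protocol 8.5.2 names the same family of test. Neither gives strata or a covariate. On adjustment, SAP 9.1 says only: "The primary model will include the stratification factors (age group and gender) used in the randomisation as covariates". Pre-operative mRS is missing from the baseline variables in SAP 5 and SAP 10. The table plan (SAP 19.3) has mRS tables for D90 only. Listing 16.2.23 covers mRS by patient and may show the D0 value. SAP 9 and 9.2 rule out imputation.

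**The concern.** A patient who was already disabled before the rupture is likely to score badly at D90 whatever the treatment. A comparison that ignores the earlier score counts this as noise, and any chance imbalance between arms goes into the estimated effect. The interim after which the study stopped had 35 evaluable patients, about 23 active and 12 placebo under 2:1 allocation. At that size, one or two previously disabled patients make up 8% to 17% of the placebo arm (1/12 and 2/12). The mRS is the trial's only functional outcome. As planned, no summary table shows whether the arms began with similar disability. The value is collected anyway, so using it needs no extra data.

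The neighbouring analyses do address adjustment. The D30 mortality result is given adjusted and unadjusted, and the D90 Cox model includes the stratification factors if feasible. The mRS sentence says nothing either way.

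**Working it through.** **The plan's own figures.** The documents give no sample size, power or precision for mRS. Those for D30 mortality hold up approximately. For 37% versus 15%, 2:1, two-sided 0.05 and 80% power, the standard formula gives 44 + 88 = 132 against the stated 129. Power at 43:86 is 79.2%. Then 129/0.85 = 151.8, which rounds up to the stated 152. These figures serve here only to set the size of effect.

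**Inputs from the documents.** 35 evaluable patients (SAP 2); 2:1 allocation, so 35 × 2/3 = 23.3 and 35 × 1/3 = 11.7, taken as 23:12; mortality of 37% and 15% (SAP 6); death scored 6 (protocol Table 9).

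**Assumptions.** The final number of patients with a D90 mRS is not given, so 35 stands in for it. D90 mRS comes from a latent normal variable with 37% dead on placebo. Pre-operative mRS is 50/30/12/5/3% in categories 0 to 4. The treatment shift is the one that turns 37% dead into 15%: Φ⁻¹(0.85) − Φ⁻¹(0.63) = 1.036 − 0.332 = 0.70. This is the plan's full D30 mortality effect carried over to D90 mRS. The correlation between pre-operative and D90 status is not in the documents, so it is varied.

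**What adjustment can do in principle.** With observed correlation ρ, it multiplies the variance by 1 − ρ². Estimating one slope in about 35 patients costs roughly a factor 1 + 1/(35 − 4) = 1.032. The net factor is:

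- ρ = 0: 1.032
- ρ = 0.2: 0.96 × 1.032 = 0.991
- ρ = 0.3: 0.91 × 1.032 = 0.939
- ρ = 0.5: 0.75 × 1.032 = 0.774

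Break-even is at ρ² = 1/32, so ρ is about 0.18. Below that, adjustment costs slightly more than it returns.

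**Simulated power.** The mean-score statistic is Z = (sum of active-arm scores − n₁ × overall mean) / √(n₁n₀s²/n), tested at two-sided 5%. The unadjusted score is the rank of D90 mRS. The adjusted score is the residual from regressing that rank on the rank of pre-operative mRS.

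| Latent correlation | Unadjusted | Adjusted | Change |
|---|---|---|---|
| 0 | 43.4% | 42.1% | −1.3 |
| 0.15 | 42.6% | 42.0% | −0.6 |
| 0.3 | 43.1% | 44.0% | +0.9 |
| 0.5 | 42.9% | 49.3% | +6.4 |
| 0.7 | 43.1% | 58.8% | +15.7 |

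Type I error stayed between 4.6% and 4.9%. A separate run with 40,000 trials per setting gave changes of −1.2 at 0, 0.0 at 0.2, +1.2 at 0.3, +6.4 at 0.5 and +15.6 at 0.7. The unadjusted column should not depend on the correlation, so its small movements are simulation error.

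**Missing pre-operative values.** With 20% missing and set to the median rank, power went from 43.9% to 43.0% at correlation 0, 43.6% to 43.8% at 0.3, 43.8% to 47.7% at 0.5, and 43.7% to 53.8% at 0.7. The gain shrinks but remains at the higher correlations.

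**Another method.** Stratifying the Cochran-Mantel-Haenszel test on pre-operative mRS (0, 1, 2 or more) shows the same pattern at 23:12. By observed correlation, power went from 43.7% to 41.6% at about 0, 43.4% to 42.6% at 0.16, 44.3% to 45.6% at 0.31, and 42.9% to 52.4% at 0.47.

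**The case against.** The case for leaving the plan alone is substantial. The protocol and SAP agree on the test. The D0 value is described as a reference, which does not promise a covariate. An unadjusted comparison of randomised arms is valid. All secondary analyses are declared supportive, and the study has already stopped. Death counts as 6, so much of the D90 score may reflect post-operative mortality, which could weaken the link with earlier disability.

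The covariate is also imperfect. It may be collected retrospectively with no stated time limit. After dosing, only survivors can answer for themselves, so a recalled value may depend on the outcome. Some D0 assessments may be skipped, so a value for every patient is an intention. Filling gaps with a median rank conflicts with the SAP's rule against imputation. Finally, adding a covariate now is a change made after the interim.

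All of this stands, but it limits how adjustment should be done and reported. It does not remove the case for showing an adjusted result beside the planned one, or for a baseline table.

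A reader might infer that the planned test certainly gives up precision, or that adjustment can never cost anything. The documents support neither, since they give no correlation and the simulations show a small loss when it is near zero. Nor do they support reading the planned test as biased or as breaking a commitment in the protocol.

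**Conclusion.** The gap is real and minor. A pre-operative mRS is scheduled, no planned comparison or table uses it, and the SAP does not say whether its Cochran-Mantel-Haenszel test is stratified. The planned test is valid. Adjustment would probably help, and the balance is favourable: about one point of power lost if the scores are unrelated, about one gained at a latent correlation of 0.3, and 6 to 16 gained at 0.5 to 0.7. These figures rest on the assumed 23:12 split, the assumed mRS distributions, the design mortality effect carried over to mRS, and a correlation that has to be assumed. The gain at 0.7 should not be quoted as the expected benefit. The endpoint is supportive, so the trial's main conclusion does not depend on it.

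**What to change.** Before database lock, amend SAP 10, 12.2 and 19.3 as follows.

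- Tabulate D0 mRS by arm, with the number missing and the number obtained retrospectively after the first dose.
- Keep the planned unadjusted test, and state whether it uses strata.
- Beside it, add a supportive mean-score test on the residuals of ranked D90 mRS (death = 6) regressed on ranked pre-operative mRS.
- State whether age group and sex enter that regression.
- Flag D0 values obtained after the first dose, and repeat the adjusted test without them.
- Give the rule for missing D0 values, for example median rank, as an explicit exception to the no-imputation rule in SAP 9 and 9.2.
- Record the addition in SAP 15 as made after the interim analysis, and label it supportive.

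The cost is a few lines of code, one baseline table and one further results table for each analysis set. No new data are needed. The remaining drawbacks are the possible one-point loss of power in the added test and recall bias in retrospective values, which the repeat analysis exposes but cannot cure.
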